Investigators should rule out the possibility of pseudo-hyponatremia due to elevated glucose (or monoclonal protein) levels. Abnormal serum sodium levels should be corrected. Adequate fluid and caloric intake, including electrolyte-rich beverages instead of plain water, has led to reversal of hyponatremia. Diuretic use should be addressed and possibly stopped, and salt supplements should be considered if hyponatremia persists

Confusional State

Confusion is usually multifactorial with associated events including older age, dehydration, electrolyte abnormalities, anemia, diarrhea, infection, concomitant medications, other comorbidities and/or high tumor burden. Optimization of fluid status, electrolytes, hemoglobin levels, thyroid function, and concomitant medications should be undertaken. Glucocorticoids should be suspected and splitting the glucocorticoid dose over 2 days may be helpful. Other CNS-active agents should also be evaluated. However, confusion can be an isolated and dose-dependent event and thus a direct role for selinexor, which crosses the blood brain barrier, cannot be ruled out. Dose reduction of selinexor may be undertaken when other causes have been ruled out. If confusion resolves and patient returns to at least baseline status, cautious re-escalation of selinexor may be attempted.

Renal Insufficiency

Baseline renal insufficiency does not appear to affect tolerability of selinexor and renal dysfunction should not preclude continued dosing with selinexor, even for patients on dialysis. If a patient is undergoing dialysis, selinexor should be given after the dialysis procedure because the effect of dialysis on selinexor plasma levels has not yet been studied. Selinexor can lead to increased creatinine, and the majority of these cases are associated with hypovolemic conditions (i.e., represent “pre-renal” azotemia). Dose modifications or interruptions and appropriate hydration typically reverse the increased creatinine.

Vision Blurred and Cataracts

Patients reporting blurry vision or other visual changes should be evaluated by an ophthalmologist. Nearly all cases of treatment-emergent visual changes have not been associated with objective findings. Changes in lens prescriptions and/or wetting drops may improve vision. Blurred vision associated with selinexor use is typically self-limited, and dosing can usually be maintained at the same level and frequency.

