As selinexor is metabolized by glutathione (GSH) conjugation, it is possible, but not demonstrated, that hepatic GSH depletion might occur in case of extreme overdose. Therefore, in patients who develop liver function test abnormalities, supportive measures such as S-adenosylmethionine (SAM) or other drugs that can replace GSH might be considered as part of the overall management plan.

Management guidelines for other selinexor-related AEs are provided in Table 4 below.

Table 4: Supportive Care and Selinexor Dose Adjustment Guidelines for AEs related to Selinexor^{a,b,c}

Toxicity and Intensity	Supportive Care and Dose Adjustment Guidelines
Fatigue	
Grade 1	
Maintain dose. Rule out other causes. If found to be anemic and symptomatic, consider transfusing even with hemoglobin >8 g/dL (anemia Grade <3).
 
Patients with significant fatigue after several doses of selinexor may have an antitumor response. Consider an unscheduled assessment of tumor response as part of the patient's evaluation.

Grade 2 lasting ≤7 days	
As per the NCCN guidelines, consider stimulants such as methylphenidate 5mg QD in the morning only.

Grade 2 lasting >7 days or Grade 3	
Rule out other causes. If found to be anemic and symptomatic, consider transfusions for hemoglobin >8 g/dL (Grade <3); transfusions usually indicated for Hb <8 g/dL (Grade ≥3). Interrupt selinexor dosing until resolved to Grade 1 or baseline.
 
For first occurrence, restart selinexor at current dose.
 
For ≥ second occurrence, reduce selinexor by 1 dose level.
 
Patients with significant fatigue after several doses of selinexor may have an antitumor response. Consider an unscheduled assessment of tumor response as part of the patient's evaluation.
 
As per the NCCN guidelines, consider stimulants such as methylphenidate 5mg QD in the morning only.

Anorexia or Weight loss	
Grade 1 anorexia	
Maintain dose. Rule out other causes. Consider nutritional consultation and use nutritional supplements (e.g., Ensure®, Boost®).
 
For persistent symptoms, start appetite stimulants, such as olanzapine (2.5 to 5 mg PO every morning) or megestrol acetate (400 mg QD), per NCCN guidelines.

Grade 1 weight loss Grade 2 anorexia	
Initiate appetite stimulants, such as olanzapine (2.5 to 5 mg PO every morning) or megestrol acetate (400 mg QD), as per NCCN guidelines.

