Grade 2 weight loss Grade 3 anorexia, or Grade 3 weight loss	
Interrupt selinexor dosing until improved to Grade 1 or baseline and weight stabilizes. Reduce selinexor by 1 dose level.
 
Rule out other causes. Consider nutritional consultation and use nutritional supplements (e.g., Ensure®, Boost®)
 
Start appetite stimulants as above

Grade 4 anorexia	Permanently discontinue selinexor

Toxicity and Intensity	Supportive Care and Dose Adjustment Guidelines
Nausea, Acute	
Grade 1 or 2	Maintain dose. Rule out other causes. Use standard additional anti-nausea medications to supplement the protocol-required 5-HT3 antagonists. If persistent, use additional anti-nausea medications to supplement the protocol-required 5-HT3 antagonist(s). Olanzapine 2.5 to 5 mg PO every morning, per NCCN guidelines, can mitigate nausea and anorexia.
Grade 3	Rule out other causes. Use additional anti-nausea medications to supplement the protocol-required 5-HT3 antagonist(s). Olanzapine 2.5 to 5 mg PO every morning, per NCCN guidelines, can mitigate nausea and anorexia. Interrupt selinexor dosing until resolved to Grade ≤ 2 or baseline and reduce selinexor by 1 dose level. Patients with significant nausea/vomiting after several doses of selinexor may have an antitumor response. Consider an unscheduled assessment of tumor response as part of the patient's evaluation.
Hyponatremia	
Grade 1 (sodium levels < Normal to 130 mmol/L)	Maintain dose. Rule out other causes including drug (e.g., diuretic) effects. Be certain that reported sodium level is corrected for concurrent hyperglycemia (serum glucose > 150 mg/dL). Treat hyponatremia per institutional guidelines including dietary review. Provide supplemental oral and/or intravenous fluids if dehydration is present. Consider addition of salt tablets to patient's diet.
Grade 3 with sodium levels <130-120 mmol/L without symptoms	Rule out other causes including drug (e.g., diuretic) effects. Be certain that reported sodium level is corrected for concurrent hyperglycemia (serum glucose > 150 mg/dL). If (corrected) sodium is Grade ≤ 3 and continues to be asymptomatic, then patient may continue current dosing without interruption provided that IV saline and/or salt tablets are provided and patient is followed closely. If Grade 3 is persistent or worsens or does not respond to treatment, interrupt selinexor dosing until resolved to Grade 1 or baseline and reduce selinexor by 1 dose level.

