Grade 3 with sodium levels <130-120 mmol/L with symptoms or Grade 4 (<120 mmol/L)	Rule out other causes including drug (e.g., diuretic) effects. Be certain that reported sodium level is corrected for concurrent hyperglycemia (serum glucose > 150 mg/dL). Interrupt selinexor dosing until resolved to Grade 1 or baseline and without symptoms. Reduce selinexor by 1 dose level.
Diarrhea	
Grade 1	Maintain dose. Rule out other causes including drug effects. Treat per institutional guidelines with anti-diarrheals, such as loperamide.
Grade 2	Rule out other causes including drug effects. Treat per institutional guidelines with anti-diarrheals. Interrupt selinexor dosing until resolved to Grade 1 or baseline. For first occurrence, restart selinexor at current dose. For \geq second occurrence, reduce selinexor by 1 dose level.
Grade 3	Interrupt selinexor dosing until resolved to Grade 1 or baseline and patient is clinically stable. Reduce selinexor dose by 1 dose level.
Grade 4	Permanently discontinue selinexor
Thrombocytopenia	
Grade 1 or 2	Maintain dose. Rule out other causes including drug effects.
Grade 3 without bleeding	Maintain dose. Rule out other causes including drug effects.

Toxicity and Intensity	Supportive Care and Dose Adjustment Guidelines
Grade 4 without bleeding	
Rule out other causes including drug effects. Platelet transfusion is allowed if clinically indicated at the discretion of the principal investigator.
 
For first occurrence: skip 1 dose and reduce selinexor by 1 dose level.
 
If recurrent, the investigator in consultation with the Medical Monitor may decide to continue selinexor dosing without dose reductions and/or interruptions as specified above, provided that platelet counts and bleeding symptoms/signs are closely monitored. Treatment with moderate to high doses of thrombopoietin stimulating agents such as romiplostim 5 to 10 µg/kg SC weekly or eltrombopag 100 to 150 mg QD can be considered at the discretion of the principal investigator. Platelet transfusion is allowed if clinically indicated at the discretion of the principal investigator.

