Grade ≥ 3 with bleeding	
Interrupt selinexor dosing and check platelet counts weekly until the bleeding has stopped, patient is clinically stable and the platelets have recovered to Grade ≤ 3 or baseline. Platelet transfusion is allowed if clinically indicated at the discretion of the principal investigator. When resuming selinexor, reduce by 1 dose level.
 
If recurrent, unless contraindicated, start treatment with moderate to high doses of thrombopoietin stimulating agents as above.

Neutropenia	
Grade 4 neutropenia (afebrile) OR Febrile neutropenia	
Institute colony stimulating factors and prophylactic antibiotics as clinically indicated per institutional guidelines.
 
Interrupt selinexor and check neutrophils at least weekly until recovers to Grade 3 or baseline and without fever (if febrile) and the patient is clinically stable. Colony stimulating factors per institutional guidelines or at the discretion of the principal investigator. When resuming selinexor, reduce by 1 dose level.
 
If recurrent, continue colony stimulating factors, interrupt selinexor until neutrophil counts improve to Grade ≤ 3 or baseline levels. Investigator in consultation with the Medical Monitor may decide to continue selinexor dosing without dose reductions as specified above, provided that CBC and infection symptoms/signs are closely monitored.

Anemia	
Treat per institutional guidelines including blood transfusions and/or erythropoietins. Consider transfusing for symptoms with hemoglobin > 8 g/dL (Grade < 3) or for any Grade 3 (hemoglobin < 8 g/dL). If possible, maintain selinexor dose as long as patient is clinically stable, but if a dose reduction or interruption is desired, it should be done at the discretion of the treating physician and requires authorization from the principal investigator and consultation with the medical monitor if indicated.	
Other clinically significant selinexor-related adverse events	
Grade 1 or 2	Rule out other causes. Maintain dose. Start treatment and/or standard supportive care per institutional guidelines.
Grade 3	
Rule out other causes. Interrupt selinexor until recovers to Grade 2 or baseline and reduce selinexor by 1 dose level.
 
Isolated values of Grade 3 alkaline phosphatase do NOT require dose interruption. Determination of liver versus bone etiology should be made, and evaluation of gamma-glutamyl transferase, 5'-nucleotidase, or other liver enzymes should be performed.

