7.2.1 Conditions Not Requiring Selinexor Dose Reduction

The following conditions are exceptions to the dose-modification guidelines and do not require a dose reduction or delay:

- Alopecia of any grade
- Electrolyte or serum analyte (e.g., urate) abnormalities that are reversible with standard interventions
- Isolated values of Grade ≥ 3 alkaline phosphatase. Determination of liver versus bone etiology should be made, and evaluation of gamma-glutamyl transferase, 5'-nucleotidase, or other liver enzymes should be performed.

In addition, selinexor dosing may be maintained in case of grade ≥ 3 hematological or non-hematological AEs not listed above (in Section 7.2) at the discretion of the enrolling physician and after consultation with the Sponsor-Investigator and the DSMC medical monitor.

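### For severe selinexor-related hyponatremia that corrects with treatment, Section 7.2.1 read literally lifts the dose reduction that Table 4 calls for, and possibly the hold; the bullet needs a hyponatremia exception

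*Combined protocol and SAP*

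**What the plan says.** Section 7.2.1 opens its list this way: "The following conditions are exceptions to the dose-modification guidelines and do not require a dose reduction or delay". The second item is "Electrolyte or serum analyte (e.g., urate) abnormalities that are reversible with standard interventions". The item sets no ceiling on grade, does not mention symptoms, and does not set hyponatremia apart.

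Table 4 in Section 7.2 is titled "Supportive Care and Selinexor Dose Adjustment Guidelines for AEs related to Selinexor" and gives hyponatremia its own rows. For Grade 3 (sodium below 130 down to 120 mmol/L) with symptoms, or Grade 4 (below 120 mmol/L), the action is: "Interrupt selinexor dosing until resolved to Grade 1 or baseline and without symptoms. Reduce selinexor by 1 dose level". Nothing in that row depends on how the sodium responds to treatment.

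The asymptomatic Grade 3 row is more lenient. If the patient "continues to be asymptomatic, then patient may continue current dosing without interruption", subject to saline or salt tablets and close follow-up. A hold and reduction apply there only if the event persists, worsens or does not respond.

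The hyponatremia paragraph of Section 7.2 describes the condition as correctable: "Adequate fluid and caloric intake, including electrolyte-rich beverages instead of plain water, has led to reversal of hyponatremia".

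**The concern.** Sodium is an electrolyte, and the protocol itself says that hyponatremia has been reversed by simple measures. A patient whose sodium falls below 120 mmol/L on selinexor and then recovers with treatment therefore fits both the 7.2.1 bullet and the strictest hyponatremia row of Table 4. The row asks for a hold and a lower dose; the bullet says that neither is required. Two investigators could manage the same event differently, each with protocol text in support, and the one who follows 7.2.1 could resume full dosing after the category of hyponatremia that Table 4 treats most strictly.

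The literal result also sits oddly with nearby rules. The closing sentence of 7.2.1 lets dosing continue through unlisted Grade 3 or higher events only after consultation with the Sponsor-Investigator and the DSMC medical monitor. The electrolyte bullet asks for no consultation.

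**Working it through.** The plan states no figure to reproduce. The check compares the texts case by case, then works out the dose difference.

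**Selinexor-related hyponatremia**

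| Event | Table 4 | 7.2.1 read literally | Conflict? |
|---|---|---|---|
| Asymptomatic Grade 3, responds to treatment | Dosing may continue | No reduction or delay required | No |
| Symptomatic Grade 3, corrects | Hold, then one level down | No reduction or delay required | Yes |
| Grade 4, corrects | Hold, then one level down | No reduction or delay required | Yes |
| Any of these, does not correct | Hold, then one level down | Outside the bullet | No |

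**Which half of the conflict is firm.** The bullet applies to abnormalities that are reversible. There are two ways to read that word.

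- Judged after the event: until the sodium has corrected, the site does not know that the bullet applies, so the Table 4 hold stands. The row itself ends the hold at Grade 1 or baseline without symptoms. What remains in dispute is the one-level reduction.
- Judged in advance: the clinician expects correction, the bullet applies at once, and both the hold and the reduction fall away.

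The reduction is in conflict on either reading, the hold only on the second. Because dosing is once weekly, the hold changes treatment only if a dose falls due before the sodium has recovered.

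**Whether any text settles precedence.**

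- Section 7.1 sends the reader to Section 7.2 and Table 4 for specific adverse events. This favours the table but does not mention 7.2.1.
- The notes to Table 4 tie dose changes to the most severe preceding toxicity. This favours acting even after correction, but again does not mention the exception list.
- The catch-all row of Table 4 says "Isolated values of Grade 3 alkaline phosphatase do NOT require dose interruption", and 7.2.1 has almost the same bullet. Alopecia and urate have no row of their own. Together these suggest that 7.2.1 was written to relieve the catch-all row.
- The closing sentence of 7.2.1 excludes events already listed in Section 7.2, but that limit attaches to its own discretionary allowance, not to the bullets.

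These point to Table 4. None limits the electrolyte bullet, and the lead-in calls the bullets exceptions to the guidelines.

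**Dose difference.** Table 3 (patients enrolled after version 7) gives levels of 60, 40 and 20 mg once weekly. Section 6.1 sets 28-day cycles, so there are 4 doses per cycle.

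- From 40 to 20 mg: 4 × 40 = 160 mg against 4 × 20 = 80 mg per cycle; (80 − 160)/160 = −50%.
- From 60 to 40 mg: 4 × 60 = 240 mg against 4 × 40 = 160 mg per cycle; (160 − 240)/240 = −33%.

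These are full-cycle differences while the lower dose is in force, and doses omitted during a hold come on top. Under Section 6.4.1 a hold longer than 28 days ends treatment. The lower dose may be temporary: footnote b of Table 4 allows re-escalation after at least 4 weeks of stabilization, and the closing Note states no minimum wait. No onset time, hold length or re-escalation time is assumed.

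**The case against.** The best defence is that an ordinary reader would let a row graded by sodium level and symptoms prevail over a generic bullet whose only example is urate. The signals listed above support that reading, so harm requires a site to take the less natural one. This stands as evidence of intent, and it is a reason to write the intent down. It does not remove the contradiction, because the text that relaxes the rule is the one labelled an exception.

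A second defence is that both texts are guidance. Section 7.1 speaks of recommendations, the table's title speaks of guidelines, and 7.2.1 says only that action is not required. Section 6.4.1 also takes patients off treatment for events that the investigator judges injurious. Events that meet the seriousness criteria of Section 15.5.4 go to the medical monitor under Sections 15.4 and 15.6. All of this stands. A reader might infer that 7.2.1 orders full dosing to continue or forbids a hold; it does neither.

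A third defence is that few patients are exposed. About 12 patients remained to be enrolled at version 7. Hyponatremia is not among the six most common related events named in Section 3.1.4, and Section 2.3.3 attributes 5 of the 7 reductions to 40 mg to weight loss. This stands and limits the weight of the point, although absence from a list of the most common events is not a rate.

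**Conclusion.** The contradiction is real and narrow. It covers selinexor-related hyponatremia that is symptomatic Grade 3 or any Grade 4 and that corrects with standard treatment. For those events 7.2.1 read literally lifts the one-level reduction, worth 50% of the cycle dose at the 40 mg level or 33% at 60 mg while the lower dose lasts. It lifts the hold only if reversibility is judged prospectively. It deserves correction because a dosing rule followed as written drops a safety action specified elsewhere in the same section.

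Three stronger conclusions are tempting, and the documents do not support them:

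- That hyponatremia management is contradictory throughout. Asymptomatic Grade 3 that responds is handled consistently, and events that do not correct fall outside the bullet.
- That exposure would differ by 50% or 33% for the rest of treatment. Re-escalation is allowed, so the duration is unknown.
- That the trial's safety or efficacy results are affected. No event rate is given, no oversight failure is shown, and neither the sample size nor the primary analysis depends on this rule.

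The conclusion rests on a literal reading of 7.2.1 and on the absence of any stated order of precedence. That such events will be infrequent is likely but remains an assumption.

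**What to change.** Amend the second bullet of 7.2.1 to read: "Electrolyte or serum analyte (e.g., urate) abnormalities that are reversible with standard interventions", followed by *, except hyponatremia, which follows Table 4 and its footnotes*.

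This keeps continued dosing for asymptomatic Grade 3 that responds, because the Table 4 row already allows it. It restores the hold and reduction for the severe categories and leaves urate and the other electrolytes as they are.

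The exception should not be confined to selinexor-related hyponatremia. That would leave unrelated events inside the 7.2.1 exemption by contrast, although footnote c calls for permanent discontinuation for unrelated Grade 4 non-hematologic events and footnote a allows dosing through unrelated Grade 3 after consultation with the principal investigator. Referring to the footnotes keeps both rules in force.

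The cost is nine added words in the next amendment and a short memo to sites. No procedure, patient or analysis is added.

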7.3 Contraception

Patients should not become pregnant or father a child while on this study as selinexor can affect an unborn baby.

Female patients of childbearing potential must agree to use two methods of contraception (one highly effective and one effective) and have a negative serum pregnancy test at Screening

Male patients must use an effective barrier method of contraception if sexually active with a female of childbearing potential.

Highly effective methods of contraception include:

- Hormonal contraceptives (e.g., combined oral contraceptives, patch, vaginal ring, injectables, and implants)
- Intrauterine device or intrauterine system
- Vasectomy or tubal ligation

Effective methods include:

- Barrier methods of contraception (e.g., male condom, female condom, cervical cap, diaphragm, contraceptive sponge)

Notes:

- No barrier method by itself achieves a highly effective standard of contraception
- The proper use of diaphragm or cervical cap includes use of spermicide and is considered one barrier method.

- The cervical cap and contraceptive sponge are less effective in parous women.
- The use of spermicide alone is not considered a suitable barrier method for contraception.
- When used consistently and correctly, “double barrier” methods of contraception (e.g., male condom with diaphragm, male condom with cervical cap) can be used as an effective alternative to the highly effective contraception methods described above.
- Male and female condoms should not be used together as they can tear or become damaged.

Alternatively, the following fulfill the contraception requirements:

- A sexual partner who is surgically sterilized or post-menopausal.
- Total (true) abstinence (when this is in line with the preferred and usual lifestyle of the patient), is an acceptable method of contraception.

NOTE: periodic abstinence (e.g., calendar, ovulation, symptothermal, post-ovulation methods) and withdrawal are not acceptable methods of contraception.

- The method of acceptable contraception must be explained to both male and female potential patients. In order to be eligible for the study, patients must agree to use the methods of birth control described above throughout the study and for 3 months following the last dose of study treatment at the time of consent for the study.

Breastfeeding

Women should not breastfeed while on this study.

